3.8.2 Key Secondary Efficacy Endpoint Analyses

A generalized logit model will be used for the analysis of key secondary endpoints: CGI-I-AS response (at least minimally improved) and CGI-I-AS response (at least much improved). The generalized logit models will include the response variable at each visit as the dependent variable, and fixed effects for visit (Week 6 and Week 12), randomized treatment, the visit-by-treatment interaction, age group (randomization stratification variable: age 4 to 8 years versus age 9 to 12 years), and region (randomization stratification variable: US versus outside US). An unstructured Cholesky working correlation for the binary outcome variable will be assumed for the model parameter estimation, and if the model fails to converge, the sequence of covariance structures specified in Section 3.8.1 will be used, until convergence is achieved. If there is no response (at least minimally improved or at least much improved) in either treatment arm at the Week 6 visit, the generalized logit model will be substituted with a logistic regression for the Week 12 CGI-I-AS response variable with effects for the randomized treatment and the two randomization stratification variables. From the model (generalized logit or logistic regression, as appropriate), the Week 12 odds ratio will be presented along with the corresponding 95% confidence interval and 2-sided *P* value.

Descriptive statistics for the observed response (either at least minimally improved or at least much improved) will also be displayed along with the 95% CI based on a

binomial distribution. In addition, the differences in observed percentages between treatment groups will be displayed, along with the corresponding 95% CI for differences in percentages and two-sided p-value.

Sensitivity analyses will be conducted based on method of assessment collection (at least one CGI-I-AS assessment conducted remotely or no CGI-I-AS assessment conducted remotely). Descriptive statistics and a subgroup analysis of the generalized logit analysis described above will be performed.

Additionally, supportive analyses will be performed for the descriptive analysis and generalized logit model with the visit mapping described in section 3.1.8 Table 3 and separately for visit mapping using nominal visits.

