For the CGI-I Symptoms Overall domain at Week 12, the Mixed Model Repeated Measures (MMRM) analysis showed a significant improvement for OV101 compared to placebo for the OV101 groups combined ($P=0.0103$) and for the OV101 QD group ($P=0.0006$). At Week 12, subjects in the OV101 QD group showed significant improvement in CGI-I Symptoms Overall regardless of age.

For the CGI-I Sleep domain at Week 12, the MMRM analysis showed a significant improvement for OV101 compared to placebo for the OV101 groups combined ($P=0.0236$) and for the OV101 QD group ($P=0.0141$).

In post hoc analyses at Week 12, most subjects in the OV101 groups combined (54.5%) had responses of minimally improved (34.5%) or much improved (20.0%) for CGI-I Symptoms

Overall, compared to 22.2% of subjects in the placebo group (14.8% minimally and 7.4% much improved). The percentages of subjects with improvement were larger in the OV101 QD group (66.6%; 29.6% minimally, 37.0% much improved) than in the OV101 BID group (42.8%; 32.1% minimally, 10.7% much improved).

NEPTUNE (OV101-19-001) will be a multicenter, randomized, placebo-controlled, parallel-group study to evaluate the efficacy and safety of OV101 in pediatric subjects with AS. Subjects who complete the study will be eligible to enroll in the ongoing OV101-18-002 (ELARA) open-label extension study, provided they meet the eligibility criteria for ELARA.

2 Study Objectives

All efficacy study objectives will be assessed in the pediatric AS study population of subjects who are 4 to 12 years old. All safety study objectives will be assessed in the pediatric AS study population of subjects who are 2 to 12 years old.

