2.2.1 Number of Subjects

Approximately 90 subjects 4 to 12 years old (inclusive) will be randomized into this study, with approximately 45 subjects in the placebo group and 45 subjects in the OV101 treatment group. The sample size determination is described in Section 7.3 of the Protocol. Approximately 5 subjects 2 to 3 years old (inclusive) will be included and treated with OV101.

The study will be conducted at approximately 15 study sites and will likely involve variable numbers of subjects at each site. Enrollment will be on a competitive basis but each site will be capped at 12 subjects (unless authorized by the Sponsor).

Activation of study sites will be centrally controlled by interactive web response system (IWRS). Subject randomization will be deactivated for all sites when the planned number of subjects is met.

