3.1.3 Statistical Testing and Significance Level

The primary efficacy analysis will be performed on the full analysis set (FAS) and the per protocol set (PPS), which are defined in Section 3.2. However, the PPS analysis will only be considered a sensitivity analysis.

Inferential treatment comparison of the primary efficacy endpoint, CGI-I-AS at Week 12, will be conducted at the 0.05 level of significance using a two-tailed test. If the null hypothesis of no treatment difference for the primary endpoint is rejected, the alpha (0.05) will be passed to the significance testing for the keysecondary efficacy endpoints (added to fulfill an EMA recommendation for responder analysis), CGI-I-AS response (at least minimally improved) at Week 12 and CGI-I-AS response (at least much improved) at Week 12, which will be tested using the corresponding 2-sided tests at 0.05 level of significance in a fixed sequence. If and only if the null hypothesis of no treatment difference based on CGI-I-AS response (at least minimally improved) is rejected at 0.05 level of significance, testing will continue and the null

hypothesis of no treatment difference based on CGI-I-AS response (at least much improved) will be tested at 0.05 level of significance.

No formal statistical testing of other secondary endpoints will be performed. The p-values presented for other secondary and tertiary endpoints will not be adjusted for multiplicity and will be considered descriptive in nature.

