3.3.2 Key Secondary Efficacy Endpoint

[figure not shown]
- CGI-I-AS response (at least minimally improved) defined as CGI-I-AS score of 1, 2, or 3 at Week 12
- CGI-I-AS response (at least much improved) defined as CGI-I-AS score of 1 or 2 at Week 12

[figure not shown]
The key secondary endpoints will be utilized to fulfill a recommendation of EMA for a responder analysis.

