5 PROGRAMMING SPECIFICATIONS

5.1 Analysis Specifications

Sample SAS code for the MMRM ANCOVA analysis is as follows:

```
proc mixed data=temp method=reml;
  class subject visit treat agegrp region;
  model endpoint = visit treat agegrp region baseline
  visit*treat ;
  repeated visit / subject=subject type=covstruc;
  lsmeans visit*treat / diff=all cl alpha=0.05;
run;
```

Use the following sequence for choosing a covariance structure, covstruc.

Use the first covariance structure that converges:

SAS Name for Covariance Structure	Covariance Description
UN	Unstructured
TOEPH	Heterogeneous Toeplitz
ARH(1)	Heterogeneous Autoregressive(1)
CSH	Heterogeneous Compound Symmetry
TOEP	Toeplitz
AR(1)	Autoregressive(1)
CS	Compound Symmetry

If the model converges with an unstructured covariance matrix, the Kenward-Roger approximation will be used to estimate the denominator degrees of freedom. If a structured covariance is used for the model, then a robust sandwich estimator will be utilized for estimating the variance of the treatment effect estimate.

For the MMRM ANOVA model, baseline is excluded from the model statement.

Sample SAS code for the generalized logit model analysis is as follows:

```
PROC GLIMMIX DATA = xxx;
  CLASS subject visit treat agegrp region;
  MODEL endpoint = visit treat agegrp region visit*treat /
  DIST= b link=logit;
  random intercept / subject=subject type = covstruc;
  LSMEANS visit*treat / diff exp cl or;
RUN;
```

Use the sequence for choosing a covariance structure, covstruc, described above with the unstructured covariance replaced by an unstructured Cholesky covariance.

Sample SAS code for the logistic analysis is as follows:

```
PROC LOGISTIC DATA = xxx;  
  CLASS treat agegrp region;  
  MODEL endpoint = treat agegrp region;  
  LSMEANS treat / diff cl or;  
RUN;
```

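### The SAP's Wald test for the last confirmatory endpoint, at least much improved, is far below 5% size if responders are as rare as in STARS, and cannot reject if no placebo child responds at Week 12

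*SAP*

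**What the plan says.** The endpoint is binary: "CGI-I-AS response (at least much improved) defined as CGI-I-AS score of 1 or 2 at Week 12" (SAP 3.3.2). It closes the confirmatory sequence. The two key secondary endpoints follow the primary, "which will be tested using the corresponding 2-sided tests at 0.05 level of significance in a fixed sequence", and once at least minimally improved has been rejected, the "hypothesis of no treatment difference based on CGI-I-AS response (at least much improved) will be tested at 0.05 level of significance" (SAP 3.1.3).

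SAP 3.8.2 fits a generalized logit model to the Week 6 and Week 12 responses, with visit, treatment, their interaction, age group and region. If there is no response at Week 6, it switches to a Week 12 logistic regression. From whichever model is used, "the Week 12 odds ratio will be presented along with the corresponding 95% confidence interval and 2-sided" p-value are taken. The prose does not name the test. The GLIMMIX code in SAP 5.1 requests "LSMEANS visit*treat / diff exp cl or", and the LOGISTIC code has a similar LSMEANS line. Neither asks for a score, exact or penalised test. There is no rule for an arm without responders at Week 12.

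Protocol 7.8.2 specifies GEE for the same endpoint.

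SAP 2.2.1 plans "approximately 45 subjects in the placebo group and 45 subjects in the OV101 treatment group". Protocol 4.2.3 aims for at least 80 evaluable completers. The only control rate for this response is in Protocol section 1, from STARS: 54.5% improved on OV101, "compared to 22.2% of subjects in the placebo group (14.8% minimally and 7.4% much improved").

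**The concern.** An LSMEANS difference is tested as estimate over standard error, which on the logit scale is a Wald test. Wald tests of a log odds ratio are conservative when one arm has few events, and they break down when an arm has none. At 7.4% of 45 children, about 3.3 placebo responders are expected.

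Two things are at stake. The test may give up power on the stricter of the two responder definitions. It may also return an unusable result when the data most favour OV101, which would leave the choice of test to be made after unblinding. The covariance sequence cannot help, because the divergence is in a fixed effect. The logistic substitute fails in the same way.

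**Working it through.** **Inputs.** 45 per arm (SAP 2.2.1), or 40 per arm (80 completers, assumed evenly split). Two-sided 0.05. Placebo rate 7.4%, equal to 2/27; 5% and 10% are assumed as the range. OV101 rates from STARS: 20.0% combined and 37.0% once daily. The arm percentages imply 10/27 and 3/28, hence 13/55 = 23.6% combined rather than 20.0%, so both are shown. The visible text gives no power figure for this endpoint to reproduce.

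**Tests.** With *a* OV101 and *b* placebo responders among *n* per arm, N = 2n and m = a + b:

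- Wald: z = ln[a(n−b) / (b(n−a))] / √(1/a + 1/(n−a) + 1/b + 1/(n−b)); a zero cell counts as non-rejection.
- CMH, single stratum: X² = (a − m/2)² / [n²m(N−m) / (N²(N−1))].

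**Size, by exact enumeration of all tables (no covariates).**

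| Rate in both arms | Wald, 40/arm | Wald, 45/arm | CMH, 40/arm | CMH, 45/arm |
|---|---|---|---|---|
| 5% | 0.05% | 0.10% | 4.3% | 4.1% |
| 7.4% | 0.37% | 0.64% | 5.7% | 4.5% |
| 10% | 1.2% | 1.8% | 5.9% | 4.8% |
| 15% | 3.1% | 3.8% | 5.4% | 5.3% |
| 20% | 4.1% | 4.5% | 5.1% | 5.1% |

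With age group and region in the Week 12 logistic model (6,000 simulated trials per setting), Wald size at 5 / 7.4 / 10% is 0.2 / 0.7 / 1.8% with 40 per arm and 0.3 / 1.1 / 2.5% with 45. An emulation of the two-visit random-intercept model (600-900 trials per setting) gave about 0.1-2.0%. Stratified CMH with 45 per arm (3,000 trials; assumed strata of 35/20/30/15%, each factor shifting the log odds by 0.5) gave 3.9 / 5.5 / 5.4%.

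**Power, Wald vs CMH.**

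| Placebo vs OV101 | 40/arm, exact | 45/arm, exact | Simulated with strata |
|---|---|---|---|
| 7.4% vs 20% | 26% vs 39% | 33% vs 43% | 28% vs 37% (40); 36% vs 43% (45) |
| 7.4% vs 23.6% | 42% vs 54% | 51% vs 59% | not run |
| 7.4% vs 37% | 86% vs 92% | 91% vs 95% | 93% vs 95% (45) |

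For at least minimally improved (22.2% vs 54.5%, 45 per arm) both tests have 89% power.

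**Single tables, 45 per arm.**

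- 7 vs 1: ln(7×44/38) = 2.093, SE 1.092, Wald p = 0.055. CMH X² = 9/1.843 = 4.88, p = 0.027.
- 8 vs 1: 2.253/1.084, Wald p = 0.038.
- 9 vs 1: 2.398/1.078, Wald p = 0.026.
- 9 vs 0: 1/b is undefined, so Wald cannot reject. Fisher p = 0.0025, CMH p = 0.0017.
- 12 vs 0, logistic fit: log odds ratio 22.6, SE 11,763, p = 0.998.

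In the random-intercept emulation, trials with a zero arm gave |t| of about 0.1 or less, apart from five numerically degenerate fits.

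**Chance of no placebo responder.** (1−0.074)^45 = 3.1% and (1−0.074)^40 = 4.6%. At 5%: 0.95^45 = 9.9% and 0.95^40 = 12.9%.

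**The protocol's GEE at a zero cell.** With a robust standard error, the 12 vs 0 example gave a log odds ratio of 24.6 with SE 0.34, so p is near 0. Under a true null, simulated rejection was 7.8-9.8% at a 7.4% rate and 18-23% at 5%, mostly from zero cells. Applying the Week 6 substitution lowers this to about 6-8% and 11-22%, depending on whether one empty arm or two triggers it. These runs assumed an independence working correlation, a between-visit correlation of 0.6 on the latent scale, and Week 6 rates of 4-5%. They also assume that the software reports the diverged fit.

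**The case against.** The strongest reply is that the low rate is not the plan's. A reader might infer that the plan expects about 7%, but the documents state no NEPTUNE rate. The 7.4% is a post hoc figure from 27 placebo subjects in a study of ages 13 to 49, whereas NEPTUNE's efficacy population is 4 to 12. At 15% the size is already 3-4%, and at 20% or more it is near nominal. That stands, and the size and power figures are conditional on a low rate.

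A reader might also infer that the Wald p-value worsens as placebo responders become fewer. It does not in the tables that matter: with 9 OV101 responders and 3, 2, 1 on placebo it is 0.075, 0.039, 0.026. Only an exact zero flips a decision.

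NEPTUNE doses once each evening, and at the STARS once-daily rate the loss is small. A conservative test is also valid. At 45 per arm and 7.4% vs 20%, Fisher's exact test has 31% power against 33% for Wald, and 7/45 vs 1/45 fails Fisher too (p = 0.058). So the power loss is relative to an approximate test. All of this stands.

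Finally, SAP 3.8.2 also reports a difference in percentages with a p-value, so 9/45 vs 0/45 would be visible. But that p-value accompanies the descriptive statistics, names no test and has no stated place in the sequence. It does not settle the hypothesis.

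**Conclusion.** The point holds for the SAP's analysis as coded. 'Wald' is read from the SAP 5.1 code, since the prose names no test. Given a placebo rate of 5-10% and 40-45 per arm, true size is about 0.05-2.5%. The power cost relative to CMH is roughly 7-13 points at 7.4% vs 20%, about 2-6 points at 7.4% vs 37%, and little once rates reach about 15-20%. Independently of power, the SAP has no usable test if no placebo child responds at Week 12: a 3-5% chance at 7.4%, 10-13% at 5%.

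A reader might infer inflated type I error, or damage to the primary result. The documents do not support either under the SAP's code: the test errs on the conservative side, it comes last, and nothing depends on it. The false-rejection risk belongs to the protocol's GEE with a robust standard error, which is an assumption because Protocol 7.8.2 does not state the standard error. Under that assumption the two documents can give opposite conclusions on the same data.

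**What to change.** In SAP 3.8.2 and 5.1:

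1. Take the confirmatory p-value for at least much improved from a CMH test of Week 12 response, stratified by age group and region.
2. When a Week 12 arm has no responder, report the odds ratio from a Firth penalised fit with a profile-likelihood interval. Otherwise keep the model-based odds ratio, as a supportive analysis.
3. Leave the test for at least minimally improved as planned; changing it gains nothing.
4. Reconcile the protocol's GEE with the SAP's model, and state the standard error.

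An ordinary likelihood-ratio test is not a good substitute: its exact size with 45 per arm is 9.0% at a 5% rate and 7.4% at a 7.4% rate.

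The cost is SAP wording and a few lines of code before unblinding, plus a protocol amendment if the change counts as substantial under Protocol 7.1. There are two downsides. CMH uses observed Week 12 responses only, so it drops children in the full analysis set who have Week 6 data alone; the SAP's own logistic substitute does the same. CMH is also approximate, with size of about 4-6% in these checks.

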3.8.3 Other Secondary Efficacy Endpoint Analyses

For each subject, the average of daily values for each [REDACTED] will be calculated for the following visit windows:

Table 4: Analysis Visit Windows for [REDACTED]

Assessment	Analysis Visit Window (Interval in Study Days)
Baseline	< Day 1
Week 6	≥ (Week 6 Visit date – 14 days) to ≤ (Week 6 Visit Date + 7 days); or ≥ Day 22 to ≤ (End of Treatment – 1 day), for subjects who early terminate before Week 6
Week 12	≥ (Week 12 Visit date – 14 days) to (Week 12 Visit Date - 1 day); or ≥ Day 65 to ≤ (End of Treatment – 1 day), for subjects who early terminate between Week 6 and Week 12

An average measure will be calculated using all available data in the above analysis windows as follows:

1. Calculate average of all observed weekday values (AVGWKD).
2. Calculate average of all observed weekend values (AVGWKE).
3. Within a visit, if both AVGWKD and AVDWKE are non-missing, then the final average for the visit is $AVGWKD * (5/7) + AVGWKE * (2/7)$.
4. Otherwise, the final average for the visit is set to the non-missing AVGWKD or AVGWKE.

An MMRM Analysis of Covariance (ANCOVA) model for the change from Baseline will be fitted for each [REDACTED] endpoint defined above with fixed effects for visit (Weeks 6 and 12), randomized treatment, the visit-by-treatment interaction, age group (randomization stratification variable: age 4 to 8 years versus age 9 to 12 years), region (randomization stratification variable: US versus outside US), and the corresponding Baseline as a covariate. An unstructured within-subject covariance structure will be specified as the first choice. If the model converges, the Kenward-

Roger approximation will be used to estimate the denominator degrees of freedom. If the model with unstructured covariance fails to converge, the following covariance structures will be tested in this order: toeplitz with heterogeneity, autoregressive with heterogeneity by visit, compound symmetry with heterogeneous variances by visit, toeplitz, autoregressive, and compound symmetry without heterogeneous variances by visit. The first covariance structure that converges will be used for the analysis. If a structured covariance is used, then a robust sandwich estimator will be utilized for estimating the variance of the treatment effect estimate. From the model, the Week 12 difference between least squares means of OV101 and placebo groups will be presented along with the corresponding 95% confidence interval and 2-sided *P*-value.

Based on the visit average values, if more than 5% but not more than 20% of any [REDACTED] secondary endpoint are missing at Week 12, a sensitivity analysis will be conducted. Details are specified in Section 3.8.6.

An additional sensitivity analysis may be performed if visit average values at Weeks 6 or 12 are based on less than 3 days of data. In this scenario, only subjects whose visit average values are based on a minimum of 3 days of data (either weekday or weekend) will be included.

The VABS-3 Total Score (Adaptive Behavior Composite Score), domain standard scores (Communication, Socialization, Daily Living Skills, and Motor Skills domains) and their subdomain raw scores, including the Maladaptive Behavior domain subscale scores, will be assessed at Baseline and Week 12 and analyzed as continuous outcome variables. When corresponding subdomain Growth Scale Value (GSV) scores or v-Scale scores are available, the GSV and v-Scale scores will also be analyzed as a sensitivity analysis.

[figure not shown]
Change from Baseline to Week 12 in VABS-3 standard/raw score will be analyzed using an ANCOVA model with effects for randomized treatment, age group (randomization stratification variable: age 4 to 8 years versus age 9 to 12 years), region (randomization stratification variable: US versus outside US), and the corresponding Baseline as a covariate. A test for a significant treatment-by-baseline interaction will be performed in a separate model (including the above terms plus the interaction term), using a 0.100 alpha level. If the treatment-by-baseline interaction is significant, then the ANCOVA assumptions are violated and an ANOVA model will be used instead. From the final model, the difference between least squares means of OV101 and placebo groups will be presented along with the corresponding 95% confidence intervals and 2-sided *P*-values.

[figure not shown]
When it is available, change from Baseline to Week 12 in VABS-3 GSV scores will be analyzed using the same method described above. Individual VABS-3 item scores and its shift from baseline at scheduled visits will be summarized in exploratory analysis.

Scatterplots to assess correlation between VABS-3 Total Score with CGI-S-AS overall at each visit (Baseline and Week 12), and change from Baseline to Week 12 in VABS-3 Total Score with change from Baseline to Week 12 CGI-S-AS will also be explored.

The CGI-S-AS assessment will be collected at Baseline, Week 6, and Week 12 and will be treated as a continuous outcome variable. An MMRM ANCOVA methodology similar to the one described previously for [REDACTED] variables will be used to analyze the change from Baseline in CGI-S-AS score.

The relationships between CGI-S-AS overall score at baseline and CGI-I-AS at Week 12 will be explored through calculation of Pearson correlation coefficient and the associated CI within each treatment group accompanied by the corresponding scatterplot to aid interpretation of the correlation. The relationships between each of CGI-S-AS domain scores at baseline and CGI-I-AS at Week 12 will also be explored using a similar approach.

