Endpoints based on composite and subdomain scores from VABS-3 assessments will be analyzed as continuous outcome variables using an ANCOVA model with effects for randomized treatment, age group, region, and the corresponding baseline as a covariate. A test for a significant treatment-by-baseline interaction will be performed in a separate model (including the above terms plus the interaction term), using a 0.100 alpha level. If the treatment-by-baseline interaction is significant, then the ANCOVA assumptions are violated and an ANOVA model will be used instead. From the final model(s), the difference between least squared means of OV101 and placebo groups will be presented along with the corresponding 95% confidence intervals and 2-sided *P* values.

Descriptive statistics will be used to summarize all safety endpoints by treatment group. Two-sided 95% CIs will be presented where meaningful. Data summaries will be displayed for incidence of AEs, clinical laboratory variables, vital signs, body weight and body mass index, physical examinations, suicidality assessed by ABC-I, and seizure diary data.

[figure not shown]
For AEs, all treatment-emergent AEs (TEAEs) will be coded using Medical Dictionary for Regulatory Activities (MedDRA) and will be summarized by MedDRA system organ class and preferred term and treatment group. Detailed listings of TEAEs, SAEs, related AEs, and discontinuations due to AEs will be provided. The incidence of TEAEs, discontinuations due to TEAEs, drug-related, and serious TEAEs will be summarized. Incidence of TEAEs by severity and relationship to study drug will also be presented. Incidence of TEAEs will be summarized separately for subjects 2 to 3 years old (inclusive). Other safety data for subjects 2 to 3 years old (inclusive) will only be presented in listings and will be displayed in by -subject graphs, as appropriate.

For clinical laboratory tests, changes from baseline to each post baseline visit with respect to clinical chemistry and hematology results will be summarized descriptively. Each laboratory parameter will be classified as low, normal, or high relative to the parameter's reference range and will be summarized with shift tables. Listings of subjects with abnormal results will be provided.

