7.1 General Considerations

All statistical analyses will be performed using SAS[®] Version 9.4 or higher. All clinical study data will be presented in subject data listings. Data summaries will be presented for all endpoints and will include descriptive statistics (number of subjects, mean, SD, first quartile, median, third quartile, minimum, and maximum) for continuous variables, and frequency and percentage for categorical and ordinal variables. If there are missing values, the number of missing values will be presented, but without a percentage.

For all analyses, “baseline” refers to the most recent non-missing value obtained immediately prior to administration of first dose, unless it is otherwise clearly defined.

Any substantial change to the data analysis methods described in the protocol will require an amendment. Any other change to the data analysis methods described in the protocol, and the justification for making the change, will be described in the SAP. Additional post hoc analyses of the data may be conducted as deemed appropriate.

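### The VABS-3 rule that swaps ANCOVA for ANOVA after a treatment-by-baseline test at 0.10 does not deal with unequal slopes, costs precision, and can leave scores of one instrument, including a raw score and its GSV check, reported from different models

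*SAP*

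**What the plan says.** SAP 3.8.3 states: "Change from Baseline to Week 12 in VABS-3 standard/raw score will be analyzed using an ANCOVA model". The model has terms for randomised treatment, age group and region, "and the corresponding Baseline as a covariate". A separate model adds treatment-by-baseline, tested at 0.10, and then: "If the treatment-by-baseline interaction is significant, then the ANCOVA assumptions are violated and an ANOVA model will be used instead". One least-squares-mean difference, with its interval and p-value, is presented from whichever model results. Protocol 7.8.3 and the Synopsis (Statistical Methods) carry the same rule: "using a 0.100 alpha level. If the treatment-by-baseline interaction is significant, then the ANCOVA assumptions are violated".

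The rule covers the total score, the domain standard scores, the subdomain raw scores and the maladaptive subscales. For growth scale values (GSV), SAP 3.8.3 adds: "When it is available, change from Baseline to Week 12 in VABS-3 GSV scores will be analyzed using the same method described above". The same section says that, where they exist, "the GSV and v-Scale scores will also be analyzed as a sensitivity analysis". It gives no method sentence for v-Scale scores.

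The SAP does not say outright that the ANOVA outcome is change or that the test is run score by score. Both follow from the sentence on change and from each score having its own baseline covariate. Neither document requires one model across scores, carries a raw score's model over to its GSV analysis, or asks for both models to be shown.

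On inferential status, SAP 3.1.3 says: "The p-values presented for other secondary and tertiary endpoints will not be adjusted for multiplicity and will be considered descriptive in nature".

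**The concern.** The stated problem is slopes that differ between arms. The stated remedy is a model with no slope at all, which is a stronger restriction than the common slope it replaces. Baseline is dropped exactly when the data suggest that it matters, and nothing is reported on how the effect varies with it.

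The ANCOVA also did not need rescuing: with randomisation it estimates the average treatment effect whether or not the slopes are equal.

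Three things are at stake:

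- **Precision** on every switched score.
- **Comparability** across scores of one instrument, since the test is applied to each separately.
- **The meaning of the GSV sensitivity analysis.** If a raw score switches and its GSV does not, the comparison mixes a change of scale with a change of model.

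For a descriptive endpoint the estimate and interval are the result, so these matter more than the p-value. Elsewhere the plan keeps baseline with no pre-test: change in CGI-S-AS is analysed by a repeated-measures ANCOVA (SAP 3.8.3 and the code in 5.1).

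**Working it through.** The documents give no power or error figure for VABS-3, so there is none to reproduce. All correlations and slope differences below are assumptions.

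**Inputs**

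- Pre-test level 0.10 (SAP 3.8.3).
- Scores: 1 total + 4 domains + 11 subdomains + 2 maladaptive = 18 (SAP 3.3.3 and 4.1.5).
- Sample size: at least 80 evaluable (Protocol 4.2.3), so 40 per arm; about 90 randomised, 45 per arm (SAP 2.2.1).

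**1. What the switch does to the slopes.** With true slopes of change on baseline of −0.30 and +0.10, the ANOVA residuals still have slopes of −0.301 and +0.100. Nothing is repaired.

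**2. Precision.** Take baseline SD 1, equal baseline and Week 12 variances, correlation ρ, mean slope of change on baseline m, slope difference d and 1:1 allocation. In large samples the residual variances are:

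- ANCOVA: (1 − ρ²) + d²/4
- ANOVA on change: (1 − ρ²) + d²/4 + m²

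The slope difference enters both equally; ANOVA pays m² on top. With equal slopes m = ρ − 1, and the ratio is 2(1 − ρ)/(1 − ρ²) = 2/(1 + ρ). For d = 0.4, with slopes placed symmetrically about ρ − 1, the formula gives the fourth column. Simulations used 40 per arm, age and region in the models, a true effect of 0.30 and 40,000 trials per setting; results are for switched scores only.

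| ρ | SE ratio, d = 0: √(2/(1+ρ)) | Simulated | SE ratio, d = 0.4 | Simulated | SD of estimate, d = 0.4, ANOVA vs ANCOVA |
|---|---|---|---|---|---|
| 0.5 | 1.155 | 1.15 | √(1.04/0.79) = 1.147 | 1.14 | 0.231 vs 0.203 |
| 0.7 | 1.085 | 1.08 | √(0.64/0.55) = 1.079 | 1.07 | 0.180 vs 0.169 |
| 0.8 | 1.054 | 1.05 | √(0.44/0.40) = 1.049 | 1.04 | 0.149 vs 0.143 |
| 0.9 | 1.026 | 1.02 | √(0.24/0.23) = 1.022 | 1.02 | 0.112 vs 0.110 |

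The mean estimate was 0.30 under both models throughout. Coverage was 94.5–95.4% with d = 0 and 95.0–95.2% with d = 0.4. With d = 0.4 the rule fired in 62%, 77%, 88% and 98% of trials.

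**3. The rule as a whole.** With 90 subjects and an effect of 0.5 SD, at ρ = 0.5, power was 0.754, 0.744 and 0.725 for ANCOVA at d = 0, 0.3 and 0.5, against 0.741, 0.715 and 0.698 for the two-stage rule. Under the null the rule rejected in 0.040–0.056 of trials, so there is no inflation.

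**4. How often scores switch by chance.** The expected number is 18 × 0.10 = 1.8. P(at least one) = 1 − 0.9¹⁸ = 0.85 if scores are independent. With exchangeable scores correlated 0.5, 0.7 or 0.9 it was 0.786, 0.653 or 0.369 in simulation (3,000 trials, ρ = 0.8, no age or region terms).

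Counting only genuine mixtures (some scores switch, but not all), the probability was 0.76, 0.64, 0.46 or 0.25 at correlations of 0.3, 0.5, 0.7 or 0.9 between the interaction tests. The two scales agree: the tests correlate at about the square of the score correlation (0.7² = 0.49), and 0.653 sits next to 0.64.

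**5. Raw score against GSV.** If all 11 subdomains have a GSV (assumed), there are 18 + 11 = 29 tests and 2.9 switches on average. A raw score and its GSV land under different models in 0.133, 0.099 or 0.071 of pairs at correlation 0.8, 0.9 or 0.95. Times 11, that is about 1.5, 1.1 or 0.8 pairs.

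**The case against.** The difference in mean change is a valid estimate of the average effect whatever the slopes, so the fallback is inefficient, not wrong. VABS-3 is not formally tested, and coverage and type I error hold. The 15% figure applies only to a switched score at the lowest correlation considered; over the whole rule the power loss at ρ = 0.5 is about 1 to 3 points. Protocol 6.2.1.2 and SAP 4.1.5 describe good test-retest reliability, which points to the upper end of the range and a cost of roughly 2–5%. The 85% figure needs independence, which is implausible for a composite, its domains and their subdomains. A common model is partly a preference, given that the scores already differ in metric and that the Motor Skills standard score exists only through age 9.

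Most of this stands, and it bounds the size. ANOVA can also match ANCOVA: at ρ = 0.7 with a slope difference of 0.5 placed wholly in the active arm, the standard errors were 0.161 and 0.162. There the mean slope is −0.3 + 0.25 = −0.05, so m² is almost nothing. But a tie in a favourable case is not a benefit. None of these points gives a reason to prefer the switch, and none removes the mixing of models between a raw score and its own sensitivity analysis.

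**Conclusion.** The concern holds. The switch does not address the violation it names, removes no bias, and generally loses precision. It also makes the reported model depend on a test that fires in about 10% of scores by chance.

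The cost is a standard error larger by about 15% (ρ = 0.5) down to 3% (ρ = 0.9) on a chance-switched score, and the loss of a common model across the VABS-3 scores and between raw and GSV analyses. Chance baseline imbalance is part of that precision cost, not an extra one.

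This should be changed, but it is not critical: the primary and key secondary conclusions are unaffected. The sizes rest on assumed correlations, equal baseline and Week 12 variances, and 40 or 45 per arm. They do not apply directly to the Motor Skills standard score, whose sample is smaller. The raw/GSV figures also assume that all 11 subdomains have a GSV.

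**What to change.** In SAP 3.8.3, Protocol 7.8.3 and the Synopsis, delete the sentence that switches to ANOVA, and make the reporting sentence refer to the ANCOVA in place of a final model (singular in the SAP, optionally plural in the protocol). Report ANCOVA with the score's own baseline, age group and region for every VABS-3 score, including GSV scores. Say that v-Scale scores follow the same model, since the SAP gives them none.

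Keep the interaction model as supportive. Fit baseline centred at its overall mean plus baseline-by-treatment, and report the interaction estimate with its 95% interval and the treatment difference at mean baseline. With 1:1 allocation that difference will nearly repeat the ANCOVA estimate, so effects at a few prespecified baseline values would add more. It should not become the main result: with a slope difference of 0.5 and no effect, its test at mean baseline rejected in 0.068 (ρ = 0.7) and 0.088 (ρ = 0.9) of simulated trials, against 0.056 and 0.051 for ANCOVA.

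The cost is a short edit in three places, with no new data and no new model. The sponsor must settle the route, because Protocol 7.1 says: "Any substantial change to the data analysis methods described in the protocol will require an amendment". A change judged not substantial can be described and justified in the SAP. The ANOVA result is lost, but SAP 3.8 still provides unmodelled observed and change summaries by arm and visit.
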